### Inclusion Criteria

1. *Describe the criteria that define who will be **included** in the study as a numbered list:*
  1. Adults over the age of 60 years old (no upper limit)
  2. Diagnosis of chronic knee osteoarthritis with pain in at least one knee as primary condition
  3. English-speaking
  4. Willing and able to visit the Brigham and Women's Pain Management Center site to participate in the study

### Exclusion Criteria

1. *Describe the criteria that define who will be **excluded** in the study as a numbered list:*
  1. Received steroid injection within 2 weeks of VR session
  2. Unwilling to put on VR headset
  3. Diagnosed seizure disorder
  4. Cognitive impairment
  5. Hearing/visual deficit
  6. Active, contagious skin infection

7. Eye infections
8. Has a pacemaker or defibrillator
9. Has a hearing aid

### **Sub-study:**

#### Inclusion Criteria:

1. Adults ages 18 and older (no upper limit)
2. Diagnosis of fibromyalgia with a minimum baseline pain level of 3 on an NPRS
3. English-speaking
4. Willing and able to visit the Brigham and Women's Pain Management Center site on two separate occasions to participate in the sub-study

#### Exclusion Criteria:

1. Unwilling to put on VR headset
2. Experience a seizure in the last 5 years
3. Cognitive impairment
4. Hearing/visual deficit
5. Active, contagious skin infection
6. Eye infections
7. Has a pacemaker or defibrillator
8. Has a hearing aid
9. History of myocardial infarction or other serious cardiovascular condition
10. Current peripheral neuropathy

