## FORESEEABLE RISKS AND DISCOMFORTS

### Risks from VR:

Contact with objects: Participants' vision is occluded by the Virtual Reality (VR) headset. In general, they will perform the VR sitting, but the program may prompt them to move their arms and/or legs during the session.

Simulator Sickness: Some participants experience simulator sickness while in the VR experience particularly after prolonged exposure. Simulator sickness symptoms can include fatigue, headache, eye strain, difficulty focusing, increased saliva in mouth, sweating, or nausea. This risk is moderate. We have 3 methods to reduce this risk. 1) Dosage of VR for this study is between 10-20 minutes which has been reported as typically used in the literature, so risk for motion sickness is reduced. 2) Participants will complete the Simulator Sickness Questionnaire after each experience to monitor for motion sickness. 3) Participants can halt any VR at any time for any reason.

Seizures: Some people may experience severe dizziness, seizures, eye or muscle twitching or blackouts triggered by light flashes or patterns during the VR. This risk is quite small. We have 2 ways to reduce this risk: 1) People with a known risk for seizures

will be excluded from this study. 2) If a subject experiences any of these symptoms we will immediately stop the VR. We will provide any indicated immediate supportive care, we will recommend that they see a doctor, and they will be discontinued from the study.

VR headset may be uncomfortable: Some people may find wearing the headset uncomfortable. This risk is small. We have 2 methods to reduce this risk: 1) we will work with the participant to adjust the headset to be as comfortable as possible. 2) participants can stop the VR experience at any time for any reason.

Contamination: The VR headset is tightfitting and in close contact with the skin of the face. It is possible that participants may cross contaminate contagious skin or eye disorders. This risk is small. We have 2 methods to reduce this risk: 1) We will exclude people who have active, contagious skin or eye infections. 2) We will use a washable face protector for each visit. Each device will be wiped with antibacterial cleaners after each use.

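### The risk section says people with a known seizure risk are excluded, but the sub-study list bars only a seizure in the last 5 years, so a diagnosed seizure disorder with an older last seizure can enter the VR session

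*Protocol*

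**What the plan says.** Three places in the protocol bear on this.

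- **Foreseeable Risks and Discomforts, Risks from VR (Seizures).** The first of two safeguards is exclusion: "People with a known risk for seizures" "will be excluded from this study". The second is reactive: "If a subject experiences any of these symptoms we will immediately stop the VR". The section rates the hazard in these words: "This risk is quite small".
- **Exclusion Criteria (main study, knee osteoarthritis).** The seizure item is "Diagnosed seizure disorder", whatever the date of the last seizure.
- **Sub-study, Exclusion Criteria (fibromyalgia).** The seizure item is "Experience a seizure in the last 5 years". No item covers a diagnosis as such.

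The VR exposure is the same in both cohorts: Virtual Tasks (main study) and Virtual Task (sub-study) describe a guided VR meditation of 10 to 20 minutes in identical terms. Research Design and Methods plans 25 sub-study participants.

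**The concern.** The risk section tells the reader that seizure risk is handled first by keeping susceptible people out. In the sub-study the eligibility list does this only for people with a recent seizure. A standing diagnosis with a last seizure more than 5 years ago is a known risk in ordinary terms, yet nothing in the sub-study list stops that person from putting on the headset.

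What is at stake is participant safety and the accuracy of the protocol's description of its own protections, not inference. Under Sub-study Design, eligibility is settled by a phone screen, so the written list decides who enters. The main study at least collects a brief medical history at the visit (Baseline Surveys). The sub-study's Pre-intervention Tasks name no such step, so the protocol describes no second check that would pick this person up. The remaining seizure-specific safeguard, stopping the VR, works only after symptoms have begun.

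**Working it through.** There is no figure to reproduce. The check is a comparison of texts.

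**Step 1: the two exclusion lists.** The main study has 9 items and the sub-study has 10.

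- Shared topics: headset refusal, seizure, cognitive impairment, hearing or visual deficit, skin infection, eye infections, pacemaker or defibrillator, hearing aid = 8.
- Main study only: recent steroid injection = 1, and 8 + 1 = 9.
- Sub-study only: serious cardiovascular history, peripheral neuropathy = 2, and 8 + 2 = 10.
- Of the 8 shared topics, 7 are worded identically. The seizure item is the only one that differs.

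**Step 2: test cases.** Take people with no other listed condition and apply each text.

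| Person | Main-study list | Sub-study list | Risk section, ordinary reading |
|---|---|---|---|
| Diagnosed disorder, seizure within 5 years | excluded | excluded | excluded |
| Diagnosed disorder, last seizure 6 years ago | excluded | **eligible** (0 of 10 items met) | **excluded** |
| No diagnosis, one seizure within 5 years | not excluded | excluded | arguably excluded |

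The second row is the conflict. None of the other nine sub-study items would by itself remove that person.

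**Step 3: does the risk section cover the sub-study?** It is the only VR risk text, and no sub-study counterpart follows it. It relies on exclusion for one other hazard, contamination: "We will exclude people who have active, contagious skin or eye infections". Both lists carry that out in the same words, "Active, contagious skin infection" plus a separate item for eye infections. The natural reading is that the section describes both cohorts. If it did not, the sub-study would have no stated mitigation for VR risks at all, which would be worse than the mismatch.

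**The case against.** The strongest reply is that known risk is never defined. A risk summary is general, the eligibility lists are operational, and a 5-year seizure history is a reasonable way to put the idea into practice. The sub-study list was clearly edited and not merely copied: one item was dropped and two were added. Rewriting a single shared item with a specific window therefore looks like a decision. This is plausible and cannot be ruled out. But the protocol states no such definition and gives no reason why the same exposure needs a different rule in fibromyalgia. Even if the window is deliberate, the risk section then misdescribes who is kept out, so one of the two texts still needs correcting.

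A second point stands in part. The main-study item is not a perfect benchmark, because it misses a recent seizure without a diagnosis, which the sub-study item catches. The sub-study rule is thus narrower in one direction and broader in the other. That does not close the gap for the person with a diagnosis and an older seizure.

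Third, the scope of the risk section is not beyond doubt: it says nothing about the quantitative sensory testing done only in the sub-study, and the payment text under Recruitment Procedures fits only the main study's single visit and follow-up survey. This suggests that some shared sections were not updated when the sub-study was added. It bears on which text to correct, not on whether they disagree.

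Finally, there are mitigations beyond exclusion. Sessions are short and supervised, and participants can stop at any time and choose among VR experiences. Anyone with symptoms receives supportive care, is advised to see a doctor and is discontinued, and the investigators review safety weekly. All of this limits the consequence, and none of it keeps the person out of the session.

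**Conclusion.** The concern holds. For one group, people with a diagnosed seizure disorder whose last seizure was more than 5 years ago, the sub-study's written criteria are narrower than the safeguard the protocol states.

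The size is modest. The document gives no figure for the group; it is narrow and can arise only among the 25 planned sub-study participants. No endpoint, estimate, sample size or error rate depends on it.

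The conclusion rests on two readings: that the risk section applies to both cohorts, and that a standing diagnosis counts as a known risk. Both are the ordinary reading, and the main-study list supports the second by excluding on diagnosis alone. Whether the 5-year window was intended cannot be settled from the protocol. The texts should be brought into line either way.

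**What to change.** Preferred: reword the second sub-study exclusion as *any diagnosed seizure disorder, whatever the date of the last seizure, or any seizure within the past 5 years*. This keeps the sponsor's own rule, closes the gap and matches the risk section. It costs one line and possibly a few eligible participants.

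Alternative, if the 5-year window is deliberate: leave the list as it is and change the first seizure safeguard in the risk section to state what is excluded in each cohort, with a short reason for the narrower sub-study rule. This costs one sentence and no participants, but leaves the group eligible.

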### **Study Design:**

Potential subjects that are interested in the study will be contacted, research staff will describe the study and go through a phone screen to make sure the subject is eligible to participate. The day before the visit the subject will be contacted and will be read the Research Participant COVID-19 Screening Questionnaire. If they answer “Yes” to any questions between 2-5 they will need to contact research staff and reschedule their session time.

#### Baseline Surveys

At the in-person visit the participant will complete the following baseline questionnaires collected via paper and pencil or REDCap, demographics, brief medical history, past experience with VR, the Pain Catastrophizing Scale (PCS), Survey of Pain Attitudes (SOPA), the Positive and Negative Affect Scale (PANAS), the PROMIS Emotional Distress Short Form, and the Brief Pain Inventory-Short Form. Answering the surveys will take 10-20 minutes.

#### Virtual Tasks

Participants will engage and follow along with a 10-20 minute guided meditation through the VR. The meditation program may include simulated movement, relaxing music, and the voice of a meditation guide. The research team member will supervise the session,

ensuring safety of the subject is maintained.

#### Post-Intervention Surveys

After the intervention, the subject will spend about 10-20-minutes filling out post-intervention questionnaires via paper or electronically via REDCap. The questionnaires include, the subject's VR experience, the User Engagement Scale, the Igroup Presence Questionnaire, the Simulator Sickness Symptoms, the Meditation Experience Questionnaire, 2 Numeric Rating Scale for pain, the PANAS, and the Patient Global Impression of Change (PGIC). Then, we will ask a short set of open-ended questions related to overall experience with the VR and meditation, feedback about the session, and willingness to utilize this intervention again. We will audio tape the responses.

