### SPECIFIC AIMS

1. The purpose of this project is to evaluate the feasibility and effectiveness of VR as a treatment option for older adults with chronic osteoarthritic knee pain.
2. Aim 1: Implement a pilot study and collect data on the feasibility of VR and its effects on pain for older adults with chronic osteoarthritic knee pain.
3. Aim 2: Analyze the feasibility of VR for this population, including looking at simulation sickness factors and drop out reasons/rates, and its impact on chronic pain immediately prior to and immediately post intervention, as well as a few days post intervention.
4. Sub-study Aim 1: The aim of this sub-study is to compare the effectiveness of a virtual reality meditation session and a non-immersive meditation session for improving pain, affect, and physiological vital stats in adults with fibromyalgia.
5. Sub-study Aim 2: We hypothesize that the VR meditation session will facilitate greater improvements in pain, affect, and physiological vital stats as compared to the non-immersive meditation intervention.

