## RESEARCH DESIGN AND METHODS

We will recruit 25 older adults with knee osteoarthritis from Brigham and Women's Hospital (BWH) to obtain 20 subjects with complete data collection. The sub-study will enroll 25 adults with fibromyalgia from BWH.

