#### Follow-Up Questionnaires

Prior to ending the session we will determine if the subject prefers to complete the follow-up questions by phone or by electronic questionnaire. Within a few days after the intervention, we will contact the participant via their preferred method to complete the surveys at home. These surveys include, the BPI-SF, the PGIC, the PANAS, the PROMIS Emotional Distress Short Forms for anxiety, depression and anger, the PCS. If we have not heard from subject within 24 hours after sending the follow-up surveys, we will contact participants to remind or assist them with completing follow-up questionnaires. These surveys will take about 10-20 minutes to complete.

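### In the main knee osteoarthritis study simulator sickness is scored only after VR, with no pre-session score and no comparator session, so a raised score cannot be attributed to the VR session

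*Protocol*

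**What the plan says.** The protocol's Specific Aims put simulator sickness into the feasibility analysis of the main study: Aim 2 is described as "including looking at simulation sickness factors and drop out reasons/rates".

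The main-study schedule is as follows.

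- Baseline Surveys: demographics, brief medical history, past VR experience, the PCS and the SOPA, then "the Positive and Negative Affect Scale (PANAS), the PROMIS Emotional Distress Short Form, and the Brief Pain Inventory-Short Form". No simulator sickness instrument is listed.
- Virtual Tasks: one VR session and nothing to compare it with. "Participants will engage and follow along with a 10-20 minute guided meditation through the VR".
- Post-Intervention Surveys: the list includes "the Igroup Presence Questionnaire, the Simulator Sickness Symptoms, the Meditation Experience Questionnaire". Audio-taped open-ended questions about the experience follow.
- Follow-Up Questionnaires: the BPI-SF, PGIC and PANAS, then "the PROMIS Emotional Distress Short Forms for anxiety, depression and anger, the PCS". Simulator sickness is not listed.

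Foreseeable Risks and Discomforts confirms that the questionnaire is completed after the experience, as a safety check. It rates the risk as moderate and gives the symptoms as fatigue, headache, eye strain, difficulty focusing, increased saliva, sweating and nausea.

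**The concern.** None of the listed symptoms is specific to VR. The main-study exclusion criteria cover visual deficit and eye infection, which bear on some causes of eye symptoms. The other entries (for example "Diagnosed seizure disorder") are aimed elsewhere, and nothing removes a person who arrives tired, with a headache or nauseated. The medical history may record a long-standing complaint, but it is not a score on the same scale on the same day. Participants also work through questionnaires before VR ("Answering the surveys will take 10-20 minutes"), which could itself cause mild fatigue or eye strain.

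A single post-session score therefore mixes symptoms present before the headset went on with symptoms that arose over the session. At stake is the tolerability part of Aim 2. If many participants report symptoms, the study has no quantitative way to say how many were new. This is a matter of data collection, which the protocol's schedule fixes, and no later analysis can recover a baseline that was not taken.

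**Working it through.** The protocol gives no symptom rate, scoring rule or threshold for simulator sickness, so there is no stated figure to reproduce. The check has three parts.

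**1. When each measure is taken in the main study**

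| Measure | Before VR | After VR | Follow-up |
|---|---|---|---|
| Simulator sickness | no | yes | no |
| PANAS | yes | yes | yes |

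The PANAS shows that the protocol already measures before and after the session where change matters. The only non-VR session in the document belongs to the fibromyalgia sub-study. That is a different population, and its pre-intervention tasks contain no simulator sickness score either.

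**2. A bound that needs no assumed background rate**

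Input: n = 20, from Research Design and Methods (25 recruited "to obtain 20 subjects with complete data collection"). Assumptions: each person is scored yes or no for reporting a listed symptom, and the values of k are illustrative.

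Each of the k people symptomatic after VR is new, worsened, unchanged or improved relative to before. The number new or worsened therefore lies in [0, k], and the post-session score does not narrow that range. Clopper-Pearson 95% intervals at the two ends:

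| k of 20 | Lower end | Upper end |
|---|---|---|
| 2 | 0/20 = 0% (0% to 16.8%) | 2/20 = 10% (1.2% to 31.7%) |
| 6 | 0/20 = 0% (0% to 16.8%) | 6/20 = 30% (11.9% to 54.3%) |
| 10 | 0/20 = 0% (0% to 16.8%) | 10/20 = 50% (27.2% to 72.8%) |

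At k = 0 the range closes, but only for the completers observed.

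**3. The same point with assumed background rates**

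Let b be the share symptomatic before VR and v the share of the rest made symptomatic over the session, with arrival symptoms assumed to persist. The observed share is 1 − (1 − b)(1 − v), so v = 1 − (1 − observed)/(1 − b). Take 8 of 20 (40%) symptomatic afterwards:

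- b = 0: v = 1 − 0.60/1.00 = 40%
- b = 10%: v = 1 − 0.60/0.90 = 33%
- b = 20%: v = 1 − 0.60/0.80 = 25%
- b = 30%: v = 1 − 0.60/0.70 = 14%
- b = 40%: v = 1 − 0.60/0.60 = 0%

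With no session effect at all, the binomial probability of 8 or more of 20 is 0.03 at b = 20%, 0.23 at b = 30%, 0.58 at b = 40% and 0.87 at b = 50%. Every b here is an assumption. The schedule never measures it, so the same result fits anything from no session effect to one wholly due to the session.

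**The case against.** The strongest reply is that Aim 2 only undertakes to look at simulator sickness. It sets no threshold, test or causal claim, and how people feel when the headset comes off is itself a feasibility result. This stands. A reader might infer that a high score would be uninterpretable, but the protocol does not support that: the score still describes symptom burden, and what is missing is attribution to VR.

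Second, the protocol has other sources: the open-ended questions, a supervised session and drop-out reasons. Participants may say that a symptom came on during VR. This also stands as a mitigation, but it is qualitative and not a score on the same scale.

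Third, the items are not shown. If they ask about change since VR, the problem is smaller. That limit is accepted.

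Fourth, the 0-to-k range is true of any post-only count, and its lower end needs every symptomatic person to have arrived symptomatic and not worsened. That is fair. The bound shows what the design leaves open and does not estimate a bias. The day-before COVID-19 screen might also remove some acutely unwell participants, but its items are not shown.

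Finally, a pre-session score does not supply a comparator. True: it separates arrival symptoms from later ones, and nothing more.

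**Conclusion.** The point holds as a low-cost design improvement. It is not a contradiction in the protocol. In the main study a raised post-session simulator sickness score cannot be attributed to the VR session, because there is neither a pre-session score nor a comparator. The size of any overstatement is unknown. Among completers the new-or-worsened count lies between 0 and k of 20, given yes/no scoring and illustrative k.

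A reader might also infer that only a high score is affected and that a low score settles tolerability. The protocol does not support that beyond completers. Its recruitment figures allow up to 25 − 20 = 5 participants (20%) without complete data. If any of them stopped because of sickness, a low score among the rest would not show it. Nothing here follows about non-completers in either direction.

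Confidence is medium, chiefly because the item wording is not shown. The post-session safety check described under Foreseeable Risks and Discomforts is adequate for its purpose.

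**What to change.** Add the same simulator sickness questionnaire at the end of the main-study baseline battery, immediately before the headset goes on. Report the post-minus-pre change and the number with new or worsened symptoms alongside the post-session score. Include participants who stop VR early wherever a post-session score exists. Describe the change as symptoms arising over the session, not as strictly caused by VR. Leave the post-session safety check unchanged.

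The cost is a few minutes per participant on top of a 10-20 minute battery, and possible priming, since asking beforehand can make people more alert to symptoms. Without a comparator, that effect cannot be removed from the change score and should be stated as a limitation.

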#### Follow-Up Questionnaires

Prior to ending the session we will determine if the subject prefers to complete the follow-up questions by phone or by electronic questionnaire. Within a few days after the intervention, we will contact the participant via their preferred method to complete the surveys at home. These surveys include, the BPI-SF, the PGIC, the PANAS, the PROMIS Emotional Distress Short Forms for anxiety, depression and anger, the PCS. If we have not heard from subject within 24 hours after sending the follow-up surveys, we will contact participants to remind or assist them with completing follow-up questionnaires. These surveys will take about 10-20 minutes to complete.

#### **Sub-study Design:**

Potential subjects that are interested in the study will be contacted, research staff will describe the study and go through a phone screen to make sure the subject is eligible to participate. The day before the visit the subject will be contacted and will be read the Research Participant COVID-19 Screening Questionnaire. If they answer "Yes" to any questions between 2-5 they will need to contact research staff and reschedule their session time

